Soiffer *et al.*⁵⁰ administered low-dose IL-2 by continuous IV infusion to 29 patients who underwent CD6-depleted BMT at least 6 weeks previously, with the intention of boosting Graft vs. Leukemia activity. Doses ranged from 0.2 to 0.6×10^6 IU/m²/day. 25/29 patients completed 4 weeks of therapy, while 17/29 patients completed at least 8 weeks of therapy. Observed toxicities included fatigue (52%), temperature $>38^\circ\text{C}$ (48%), nausea/vomiting (38%), myalgias (31%), diarrhea (24%), edema/weight gain (21%), dyspnea (21%), catheter infection (17%), thyroid dysfunction (7%), thrombocytopenia (<20,000; 7%) and neutropenia (<500; 3%). Toxicities were most prominent in patients on higher doses.

In contrast to IV administration, SC administration is associated with slower absorption with maximum concentrations occurring 2-5h after dosing, 20-30-fold lower peak serum levels and a longer elimination half-life (5h SC vs. 1.5h IV)⁴⁰, all of which may contribute to a favorable toxicity profile with SC administration.

Koreth *et al.*⁵¹ administered daily SC low-dose IL-2 to 29 patients (28 were evaluable) with steroid-resistant chronic GvHD following HSCT. The maximum tolerated dose (MTD) in this study was found to be 1×10^6 IU/m²/day. The higher dose of 3×10^6 IU/m²/day was associated with persistent grade 1 constitutional symptoms, necessitating dose reduction. Toxicities related to IL-2 included reversible induration of SC injection sites (n=3/28), grade 2 constitutional symptoms (fever, malaise and fatigue in 1/28), grade 2 renal dysfunction (1/28) and grade 2 thrombocytopenia (1/28). Two patients in this study developed thrombotic microangiopathy-associated renal failure requiring dialysis. Both of these patients received sirolimus and tacrolimus, which are associated with thrombotic microangiopathy. Three patients developed grade 3 or grade 4 infections. One patient with a background of MRSA pneumonia developed recurrent MRSA pneumonia following 7 weeks of therapy. A second patient developed

Hemophilus influenzae type-B bacteremia following 4 weeks of treatment. A third patient had a pre-existing MRSA furuncle, necessitating discontinuation of treatment at day 2.

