Data support the stability and sterility of reconstituted diluted aldesleukin preparations (reconstituted with SWFI and further diluted with D5W); and the stability and sterility of product reconstituted with SWFI but not further diluted, for up to 14 days at 2-8°C (36-46°F) when syringes are prepared by qualified health-care professionals under aseptic conditions⁴⁰. Therefore, if reconstitution and dilution are performed under controlled and validated conditions using a laminar flow hood, the dose or doses thus prepared and stored at 2-8°C (36-46°F) need to be used within 14 days.

On 4/26/2016, the Investigational Drug Service (IDS) at Brigham & Women's Hospital, Boston MA, reduced the beyond use dating for aldesleukin that is prepared at their research pharmacy for this study from 14 days to 9 days. **Consequently, aldesleukin prepared at BWH IDS and subsequently stored at 2-8°C (36-46°F) needs to be used within 9 days.**

10.4 Dosage.

Aldesleukin will be given according to the dose schema described in Section 9.2 (page 21), based on the cohort into which they are accrued. The first two subjects to receive IL-2 will be admitted overnight to the Clinical Translational Study Unit (CTSU). Aldesleukin may be administered in the home or out-subject setting by daily subcutaneous injection for 8 weeks. Subjects who receive additional treatment after experiencing clinical benefit from 8 weeks of

initial therapy may continue aldesleukin therapy at their initial dose level. They will be followed by their physician according to Section 9.7 (page 27).

10.5 Administration.

The product should be inspected visually for particulate matter or discoloration and brought to room temperature before administration. Administer as a subcutaneous injection. DO NOT ADMINISTER AS INTRAVENOUS PUSH OR BOLUS. Premedications are not required prior to the first dose or escalated doses.

11 CLINICAL AND LABORATORY EVALUATIONS.

Participants will have 10 face-to-face encounters with research staff throughout the clinical trial, including (i) Screening at week -2, (ii) Baseline assessment prior to first dose (day 0), (iii) Clinical assessment prior to second dose (day 1), (iv-viii) Assessments at day 4 optional visit) and weeks 1, 2, 4 and 6, (ix) End of treatment assessment at week 8, and (x) End of study assessment at week 12. On completion of the study, research staff will contact participants by telephone monthly for 2 months and on a 2-monthly basis for a further two months.

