Note: The following basic science investigations can be performed at the screening visit or at the baseline (Day 0) visit, at the discretion of the investigator.

- Immunology bloods: Quantitative flow cytometric assessment of leucocytes, NK cells and Treg subsets from PB and endoscopic biopsies. Assessment of PB and LP Treg function. Banking of PBMCs, plasma, RNA, DNA.
- Microbiology: Stool sample and mucosal biopsies for analysis of the intestinal microbiome.
- IL-2 serum levels and anti-aldesleukin antibodies.

11.2 Baseline, Treatment and End-of-Study Evaluations (Day 0 to Week 6 and Week 12).

The following evaluations will be performed at baseline (day 0), day 4 (optional visit), and weeks 1, 2, 4, 6 and 12:

- Medical history and physical examination, including assessment of symptoms and signs in order to detect potential drug toxicity (routine).
- Hematology: Complete blood count (CBC) and differential (routine).
- Inflammatory markers: ESR and CRP (routine).
- Serum chemistries: glucose, BUN, creatinine, uric acid, total bilirubin, alkaline phosphatase, LDH, total protein, albumin, AST, ALT, and calcium (routine).
- Thyroid function tests (TSH, T3, free T4) (week 12).
- Immunology bloods: Quantitative flow cytometric assessment of leucocytes, NK cells and Treg subsets from PB. Assessment of PB and LP Treg function. Banking of PBMCs, plasma, RNA, DNA.
- Microbiology: Stool sample for analysis of the intestinal microbiome (day 0, weeks 1, 2, 4, 6, 8 and 12).
- Fecal calprotectin (day 0, weeks 1, 2, 4, 6, 8 and 12).
- IL-2 serum levels and anti-aldesleukin antibodies (not days 1 or 4).

Participants will attend the CTSU for their first IL-2 dose on day 0 and their second IL-2 injection on day 1. Participants will be evaluated clinically at that encounter.

11.3 End of Treatment Evaluation (Week 8).

The following evaluations will be performed at week 8:

- Medical history and physical examination, including assessment of symptoms and signs in order to detect potential drug toxicity (routine).
- Flexible sigmoidoscopy and biopsies with calculation of the Mayo score. The same biopsies will be obtained as at the screening procedure, except that histology will be limited to the rectum and sigmoid/distal descending colon.
- Hematology: Complete blood count (CBC) and differential (routine).

- Inflammatory markers: ESR and CRP (routine).

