- Quantification of leucocytes and Treg subsets will be performed by flow cytometric identification of CD3, CD4, CD8, CD25, CD127, CD45RA and FOXP3 in PBMC and LPMC preparations. CD16 and CD56 expression will be used to identify NK cells.
- The biological effect of SC IL-2 on STAT5 phosphorylation in effector T cells and Tregs will be assessed by flow cytometry.
- The suppressive function of PB and LP Tregs prior to and during treatment will be evaluated by assessment of Treg-mediated inhibition of CFSE dilution, using sorted CD4⁺CD25^{hi}CD127^{lo} Tregs and freeze-thawed CFSE-labelled allogeneic CD4⁺CD25⁻ T responders.
- Intestinal microbiome analysis will be performed on snap-frozen stool and endoscopic biopsy samples. This will include phylogenetic identification and subtyping based on 16S ribosomal RNA classification and will be performed at the Harvard Digestive Disease Center Microbiome Core Facility.

11.6 Assessment of Aldesleukin Immunogenicity.

IL-2 levels and anti-aldesleukin antibodies will be determined at baseline, weeks 1, 2, 4, 6, 8 and 12. If anti-aldesleukin antibodies are detected, anti-aldesleukin antibody levels will be monitored beyond the 12-week study period until antibody levels have returned to baseline.

Table 3: Summary of Required Data

	Screening (Pre-treatment)	Days 0, 1 ^a , 4 ^b Weeks 1, 2, 4, 6	Week 8	Week 12
Medical history				
Physical examination				
Pregnancy test				
Viral testing: HIV, HBV, HCV				
Screening for TB				
Stool for C&S, O&P, C. difficile				
Colonoscopy/flexible sigmoidoscopy ¹ & Mayo score				
CBC & differential		*		
ESR, CRP		*		
Serum chemistry		*		
Thyroid function tests				
IL-2 serum levels		*		
Anti-aldesleukin antibodies		2		
Intestinal microbiome analysis ⁴		2		
Fecal calprotectin		3		
Immune phenotyping		*		
Notes. a: History and physical examination only at day 1, unless additional investigations indicated clinically. b: Day 4 visit is optional.				
1: A full colonoscopy may be performed at screening to define disease extent in addition to mucosal inflammation if the subject has never had a full colonoscopy.				
2: Not days 1 or 4. 3. Not day 1.				

11.7 Anticipated Toxicities.

The toxicities seen in clinical trials utilizing similar doses of IL-2 are shown in Table 4, below. They are also discussed in Section 4.6 (page 13).

Table 4: Anticipated Toxicities

Study	IL-2 dose	Indication	Evaluable subjects (n)	Observed toxicities	n (%)

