Soiffer et al. ⁵⁰	0.2-0.6x10 ⁶ IU/m ² /day	Enhance graft vs. leukemia effect following HSCT	29	Fatigue	15 (52)
				Temp >38°C	14 (48)
				Nausea/vomiting	11 (38)
				Myalgia	9 (31)
				Rash	9 (31)
				Diarrhea	7 (24)
				Edema	6 (21)
				Dyspnea	6 (21)
				Catheter infection	5 (17)
				Thyroid dysfunction	2 (7)
Koreth et al. ⁵¹	0.3-3x10 ⁶ IU/m ² /day	Treatment of steroid-resistant GvHD	28	Thrombocytopenia	2 (7)
				Injection site induration	3 (11)
				Infections*	3 (11)
				Renal failure**	2 (7)
				Renal dysfunction	1 (4)
				Flu-like symptoms	1 (4)
				Thrombocytopenia	1 (4)
Saadoun et al. ⁵²	1.5-3x10 ⁶ IU/day	Treatment of HCV-associated vasculitis	10	Fatigue	4 (40)
				Flu-like symptoms	4 (40)
				Injection site induration	2 (20)
				Arterial hypertension	1 (10)
				Myalgia	1 (10)

* Recurrent MRSA pneumonia (1), *Hemophilus influenzae* type-B bacteremia (1), MRSA furuncle (1)

** Thrombotic microangiopathic renal failure in two subjects taking tacrolimus and sirolimus. This is a recognized complication of this combination of medications.

11.8 Criteria for Treatment Discontinuation.

Subjects will be removed from the study and therapy with IL-2 should be abandoned for any of the following circumstances if they are deemed possibly, probably or definitely related to IL-2, or per subject preference:

- The subject withdraws his/her consent at any time.
- Anaphylactic reaction to IL-2.
- Life threatening infection on IL-2.
- Other grade 4 toxic event.
- Grade 3 toxicity.
- Grade 2 renal toxicity.
- The development of toxic megacolon or colitis requiring immediate surgical intervention.
- At the discretion of the treating physician.

11.9 Dose Modification/Toxicity Management.

In the event of IL-2 related toxicity that does not meet the requirement for treatment discontinuation (grade 2 toxicity or less, excluding grade 2 renal toxicity), the treating physician may elect to withhold IL-2 to allow the toxicity to resolve. IL-2 can be recommenced at 50% of the target dose if the toxicity resolves to grade 1 or better within 2 weeks. At the discretion of the treating physician, if re-introduction of IL-2 is tolerated by the subject, the dose of can be escalated to the target dose.

12 REPORTING OF UNANTICIPATED PROBLEMS INVOLVING RISKS TO RESEARCH SUBJECTS, INCLUDING ADVERSE EVENTS.

12.1 Reporting to the Principal Investigator.

The following events will be reported to the principal investigator within 24 hours of being known:

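### Section 11.8 removes subjects with listed IL-2-related events from the study as well as from IL-2, so the outcome, duration and late effects of those events are not required to be recorded

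*Combined protocol and SAP*

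**What the plan says.** Section 11.8 orders two acts in one sentence: "Subjects will be removed from the study and therapy with IL-2 should be abandoned for any of the following circumstances". The condition attached is "if they are deemed possibly, probably or definitely related to IL-2, or per subject preference". The list covers anaphylaxis, life-threatening infection, "Other grade 4 toxic event", grade 3 toxicity, grade 2 renal toxicity, and toxic megacolon or colitis needing immediate surgery. It also covers withdrawal of consent and physician discretion.

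Section 11.9 deals with milder toxicity (grade 2 or less, apart from grade 2 renal) without removal: "the treating physician may elect to withhold IL-2 to allow the toxicity to resolve".

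Section 14.1 determines safety by assessment at study visits. Section 11 places those visits at days 0 and 1, an optional day 4, and weeks 1, 2, 4, 6, 8 and 12. It then adds: "On completion of the study, research staff will contact participants by telephone monthly for 2 months", followed by a further period at a two-month interval. Section 11.6 states: "IL-2 levels and anti-aldesleukin antibodies will be determined at baseline, weeks 1, 2, 4, 6, 8 and 12". After screening, thyroid function is listed only at week 12 (Section 11.2) and week 8 (Section 11.3).

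**The concern.** Safety is primary objective (i) in Section 5.2. A subject who tolerates IL-2 is observed for four weeks after the last scheduled dose and then contacted by telephone. A subject whose IL-2 is stopped for a listed event leaves the study on the same day, and nothing in the protocol requires further observation. The plan therefore asks for least information after the more serious related events.

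The questions left open are those a first study in this population should answer: whether renal function recovers, whether thyroid function changes, whether antibodies appear, and whether an infection or other event follows the stop. With cohorts of three to six, one case without a recorded outcome is a material gap in the safety description of a dose level.

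**Working it through.** The plan gives no figure on this point to reproduce. The check compares the sections and then counts scheduled assessments.

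**Step 1: stopping drug versus leaving the study.** Section 9.5, where it says what happens to treatment, says IL-2 is withheld (grade 3 toxicity except colitis, life-threatening infection, grade 2 renal toxicity) or discontinued (megacolon or colitis needing surgery). It does not mention leaving the study. Section 9.7 likewise stops therapy for toxicity during extended treatment. Section 11.8 alone adds removal from the study, for the same kinds of event.

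**Step 2: is follow-up provided elsewhere?**
- Section 11: the week 8 and week 12 visits belong to the study; the calls come after its completion.
- Section 11.6: monitoring beyond week 12 applies only once antibodies have been detected, and covers antibody levels only.
- Sections 9.7 and 11.4: three-monthly visits are for responders who continue IL-2 after 8 weeks.
- Sections 12 and 13: reporting and board review of known events; no assessment of the subject is scheduled.

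No section gives an early-termination visit, visits off drug, or follow-up of an event to resolution.

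**Step 3: what is no longer required.** Inputs: post-dose antibody tests at weeks 1, 2, 4, 6, 8 and 12 (six, Section 11.6); post-baseline thyroid tests at weeks 8 and 12 (two, Sections 11.2 and 11.3); clinic visits from week 1 on at the same six weeks (Section 11; optional day 4 set aside). Assessments lost = scheduled times later than the last visit attended. The marks in the cells of Table 3 are not legible in the copy used, so the count rests on the section text.

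| Removed after | Clinic visits lost | Antibody tests lost (of 6) | Thyroid tests lost (of 2) | Weeks short of week 12 |
|---|---|---|---|---|
| first days, before week 1 | 6 | 6 | 2 | more than 11 |
| week 1 | 5 | 5 | 2 | 12 − 1 = 11 |
| week 2 | 4 (weeks 4, 6, 8, 12) | 4 | 2 | 12 − 2 = 10 |
| week 4 | 3 | 3 | 2 | 12 − 4 = 8 |
| week 6 | 2 | 2 | 2 | 12 − 6 = 6 |
| week 8 | 1 | 1 | 1 | 12 − 8 = 4 |

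Anyone removed before week 8 has no scheduled post-baseline thyroid test. A subject removed for anaphylaxis in the first days has no scheduled post-dose antibody test, so the extension in Section 11.6 cannot be triggered by one.

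**Step 4: the link to DLT counting.** Section 9.4 makes a subject unevaluable who is removed from the study, or dies, without DLT before 8 weeks of IL-2. Section 9.5 does not expressly call grade 3 or grade 2 renal toxicity a DLT. Section 9.4 also equates intolerable lower-grade toxicity that prevents completion with a DLT. Take three subjects at dose level A or B, one stopped early for related grade 3 toxicity and two completing without DLT:
- Removal clause of 9.4 applied: one subject unevaluable, 0 of 2 evaluable with DLT, one more subject added.
- Counted as equivalent to a DLT: 1/3, three more subjects at the same level.
- Kept in the study with 9.4 unchanged, and not counted as equivalent: 0/3, escalate.

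The third outcome arises only if 11.8 is amended and 9.4 is not. The two sections must change together.

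**The case against.** The best defence is that Section 11.8 is loosely worded. Its heading speaks of treatment, Section 11.9 refers to the same list as grounds for discontinuing treatment, and no sentence says that visits stop. Sites may well keep seeing these patients, if only in routine care. This has force: the end of follow-up is inferred from removal plus the absence of any off-treatment schedule. But the sentence does order removal, and if only treatment was meant, no text says which assessments continue. Either way the sections need reconciling.

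A second defence is that the event itself is captured. DLTs reach the principal investigator within 24 hours (Section 12.1), the board reviews every serious event and DLT (Section 13), and a DLT once counted does not change with later visits. This stands. A reader might infer that safety data are lost for every subject with toxicity, or that the toxicity findings as a whole are censored by toxicity. The documents do not support that: the trigger is recorded, and non-renal toxicity of grade 2 or less is managed on study under Section 11.9. What is not required is outcome, duration and later events.

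A reader might also infer a head count from the infusion study in Section 4.6, where "25/29 patients completed 4 weeks of therapy, while 17/29 patients completed at least 8 weeks of therapy". That gives (29 − 25)/29 = 14% and (29 − 17)/29 = 41%, or about 4 to 12 of 28 subjects. The inference does not hold. Those are all-cause figures from continuous intravenous infusion after marrow transplantation, the planned duration is not given, and 28 is the maximum sample in Section 15.2 (Table 1 projects 3 + 3 + 16 = 22). In the subcutaneous vasculitis study in the same section, only grade 1 toxicities were seen in 10 patients.

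**Conclusion.** The point holds in a limited form. As written, Section 11.8 ends study participation for subjects with the listed IL-2-related events, and the protocol then requires no record of how the event ended, how long it lasted, or what followed. The size per subject comes from the schedule; the number of subjects affected cannot be estimated from the documents.

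Two assumptions carry the conclusion: that removal from the study means the remaining study visits are not required, and that the section text on thyroid and antibody tests reflects the intended schedule. The point does not show that any DLT would be missed at the time it triggers removal, or that the operating characteristics in Table 6 are wrong. It deserves correction because it concerns a primary objective and the remedy is mostly wording.

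**What to change.** In Section 11.8, separate stopping IL-2 from withdrawal from the study. Subjects whose IL-2 is stopped stay in for the safety assessments already scheduled through week 12 and for the telephone contacts, unless they withdraw consent or prefer to leave. The triggering event is followed until resolved or stable. State whether the week 8 endoscopy applies to subjects no longer on drug.

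In the same amendment, reconcile Sections 9.4, 9.5 and 11.8. Base DLT evaluability in 9.4 on stopping IL-2 before 8 weeks, not on removal from the study, and state how a subject stopped for grade 3 or grade 2 renal toxicity is counted. Without this, retention could turn such subjects into evaluable subjects without DLT after a truncated course. Which clinical rule applies is for the investigators; the need is for one consistent statement.

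The cost is one amendment, a few safety visits in subjects no longer on drug, and follow-up of any event still open at week 12. No dose or stopping criterion changes.

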- (xvii). Uncontrolled cardiac angina or symptomatic congestive cardiac failure (NYHA Class III or IV).

7 RULES FOR CONCOMITANT IBD MEDICATIONS.

- (i). Subjects receiving oral 5-aminosalicylates or oral corticosteroids (prednisone ≤40mg per day or its equivalent) must receive stable doses for at least 2 weeks prior to commencement of the study.
- (ii). Subjects receiving azathioprine, 6-mercaptopurine, methotrexate, cyclosporine, tacrolimus, sirolimus or mycophenolate mofetil must receive stable doses for at least 4 weeks prior to commencement of the study.
- (iii). Subjects receiving concurrent tacrolimus and sirolimus will be excluded, due to the increased risk of renal failure seen in previous studies when these medications were co-prescribed.
- (iv). Rectally administered steroids or mesalamine will be discontinued 2 weeks before screening.
- (v). Subjects receiving IV steroids or biologic agents must undergo a 4-week wash-out period prior to enrolment.

8 SUBJECT ENTRY.

8.1 Recruitment and Accrual.

Subjects enrolled in the trial will be identified through the gastroenterology department at Boston Children's Hospital.

8.2 Study Site Responsible Investigator.

Boston Children's Hospital

[name] MD PhD

Boston Children's Hospital

Division of Medicine (GI/Nutrition),

[name],

[name].

[contact]

9 TREATMENT PROGRAM.

9.1 Description of Study Design.

This is an open-label phase Ib/IIa clinical trial to determine the safety and maximum tolerated dose of daily SC IL-2 in eligible subjects with moderate to severe ulcerative colitis (UC). Subject cohorts will receive escalating dose levels of IL-2, as shown in Table 1 (page 22). A minimum of three subjects will be treated in each cohort, with an additional ten subjects treated at the presumptive MTD.

9.2 Dose Cohorts.

[figure not shown]
Koreth *et al.*⁵¹ treated subjects with steroid-resistant GvHD with doses ranging from 0.3-3.0x10⁶ IU/m²/day. Doses of 0.3 and 1.0x10⁶ IU/m²/day were well-tolerated. 1.0x10⁶ IU/m²/day was found to be the MTD in this study. Dose limiting toxicity (DLT) occurred at 3.0x10⁶ IU/m²/day. Saadoun *et al.*⁵² treated subjects with treatment-resistant HCV-associated vasculitis at a dose of 1.5x10⁶ IU/day, which was well-tolerated in this study. The side-effects seen in these studies are detailed in Section 4.6 (page 13).

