2/3	
Current dose level has not been tolerated. Reduce dose to the lower dose level
If only 3 subjects have been treated at the lower dose level, accrue an additional 3 subjects at the lower dose level.If 6 subjects have already been treated at the lower dose level, the lower dose level is the MTD.If this occurs at dose level A, the study will be terminated early.
1/3 + 0/3 (1/6)	
Escalate dose. Accrue 3 new subjects at next highest dose level. If 0/6 or 1/6 DLTs at dose level C, then this is the MTD.
1/3 + 1/3 (2/6)	
Current dose level has not been tolerated. Reduce the dose. If this occurs at the lowest dose level, the study will be terminated early.

To be read with reference to Section 9.3 (page 22), above. Adapted from Koreth *et al.*⁵¹

9.4 Determination of Maximum Tolerated Dose.

The maximum tolerated dose (MTD) is the highest tolerated dose level at which a minimum of 6 subjects have been evaluated, with fewer than 2 evaluable subjects in 6 experiencing a dose limiting toxicity (DLT); i.e. DLT in $\leq 1/6$ evaluable subjects. **In addition to the above, at least 1 patient should meet the criteria for response or remission for it to be considered the MTD.**

Subjects will be considered unevaluable for DLT if they are removed from the study or die without developing DLT prior to receiving at least 8 weeks of IL-2 therapy. If there are fewer than 3 evaluable subjects in a cohort, additional subjects will be added at that dose level.

Intolerable lower grade toxicity that does not meet the definition of DLT, but still means that a subject is unable to complete the per-protocol treatment will be taken as equivalent to a DLT for the purpose of assessing dose escalation. If ≥ 2 subjects in a cohort of 3 refuse to continue at that dose level for at least 8 weeks due to intolerable lower grade toxicity, that dose level will not be regarded as the MTD.

9.5 Definition of Dose Limiting Toxicities.

Organ toxicities will be assessed at scheduled clinical visits and graded according to the National Cancer Institute Common Terminology Criteria for Adverse Events v4.0⁵⁴.

- (i). **Anaphylaxis:** Life threatening anaphylaxis due to the study drug is considered a DLT.
- (ii). **Grade 4 toxicity:** Grade 4 toxicity (except colitis, see below) directly related to IL-2 by week ~~11~~8 of IL-2 treatment is considered a DLT.

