A Data Safety and Monitoring Board (DSMB) has been constituted. The DSMB members are as follows: [name] MD PhD (Chair, Gastroenterologist, University of North Carolina at Chapel Hill), [name] MB BS MPH (Gastroenterologist, Massachusetts General Hospital), and [name] PhD (Statistician, Boston Children's Hospital). The DSMB will determine stopping points for individual subjects and the study as a whole. In addition, the DSMB will determine the schedule of meetings in order to review subject safety information and will also make recommendations concerning the continuation, modification or termination of the study.

The DSMB will review study data and make recommendations on the conduct of the study at the following time points:

- In the event of any serious adverse events or DLT.
- When the third subject completes 8 weeks of IL-2 treatment, as per protocol.
- Three months after study initiation.
- Six months after study initiation.
- At six month intervals thereafter.

14 STUDY ENDPOINTS.

Subjects will be periodically assessed as described in Section 11 (page 31) in order to determine if the primary and secondary endpoints have been met.

14.1 Determination of Safety of Daily SC Low Dose IL-2.

The safety of daily low-dose IL-2 will be determined by assessing for potential side-effects and dose limiting toxicity at each study visit.

14.2 Determination of the Maximum Tolerated Dose of Daily SC Low Dose IL-2.

The MTD will be determined using the dose escalation strategy and assessments described in Sections 9 and 11 (pages 21 and 31, respectively).

14.3 Determination of the Feasibility of Administering an Eight Week Course of Daily SC Low Dose IL-2 in Subjects with Moderate to Severe UC.

This relates to the technical feasibility of administering daily low-dose SC IL-2 as per protocol. The narrative report of this outcome will include the numbers of subjects enrolled, subjects who completed the protocol and a description of any barriers to the technical feasibility of this approach in subjects with UC.

14.4 Determination of the Clinical Response to Daily SC Low Dose IL-2.

Mayo score^{7,55} (Table 5; page 44) will be assessed as per protocol between weeks -2 and 0 (as close to week 0 as possible) and week 8 in order to determine clinical response. Moderate to severe UC, denoted by a Mayo score of 6-12 is an inclusion criterion. Clinical response and remission are defined according to Rutgeerts *et al.*⁷

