14.4.1 Definition of Clinical Response.

“A decrease from baseline in the total Mayo score of at least 3 points and at least 30% , with an accompanying decrease in the subscore for rectal bleeding of at least 1 point or an absolute subscore for rectal bleeding of 0 or 1.”⁷

14.4.2 Definition of Remission..

“A total Mayo score of 2 points or lower, with no individual subscore exceeding 1 point.”⁷

14.4.3 Definition of Mucosal Healing.

“An absolute subscore for endoscopy of 0 or 1.”⁷

14.5 Assessment of the Immunological Response to IL-2 Therapy.

Data obtained from research laboratory-based assessment of subject immune responses to IL-2 therapy, that do not have direct clinical relevance, will be reported as appropriate for each data type.

Table 5: Mayo Scoring System for Assessment of Ulcerative Colitis Activity.^{7,55}

Stool frequency*	
0	Normal no. of stools for this subject
1	1 to 2 stools more than normal
2	3 to 4 stools more than normal
3	5 or more stools more than normal
Rectal bleeding**	
0	No blood seen
1	Streaks of blood with stool less than half the time
2	Obvious blood with stool most of the time
3	Blood alone passes
Findings on endoscopy	
0	Normal or inactive disease
1	Mild disease (erythema, decreased vascular pattern, mild friability) ^[1,2]
2	Moderate disease (marked erythema, lack of vascular pattern, friability, erosions) ^[1,2]
3	Severe disease (spontaneous bleeding, ulceration)
Physician’s global assessment	
0	Normal
1	Mild disease
2	Moderate disease

3 Severe disease

- * Each subject serves as their own control.
- ** Represents the most severe bleeding of the day.

15 STATISTICAL CONSIDERATIONS.

The primary endpoint of this Phase I study is to determine the MTD of daily subcutaneous IL-2 in moderate to severe UC.

15.1 Probability of Dose Escalation Under Various DLT Rates.

Table 6 shows the probability of escalation under various true DLT rates. With this design, there is 91% probability of escalation if the true rate of DLT is 10% and 17% probability of escalation if the true DLT rate is 50%.

Table 6: Probability of Dose Escalation	
True rate of DLT	Probability of dose escalation
10%	0.91
20%	0.71
30%	0.49
40%	0.31
50%	0.17
60%	0.08

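### No rule stops a response that follows a UC drug change before week 8 from being the one responder required for the MTD; the response rate also has no stated denominator

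*Combined protocol and SAP*

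**What the plan says.** **Outcome.** Section 14.4 compares the Mayo score at baseline and week 8; the timing is given as "as close to week 0 as possible) and week 8 in order to determine clinical response". Section 14.4.1 defines response as "A decrease from baseline in the total Mayo score of at least 3 points and at least 30" per cent, plus a rectal bleeding criterion. Remission (14.4.2) and mucosal healing (14.4.3) are also defined from Mayo scores or subscores. None of these definitions refers to concomitant drugs.

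**UC drugs.** Under Section 7(i), subjects on oral 5-aminosalicylates or oral corticosteroids "must receive stable doses for at least 2 weeks prior to commencement of the study". The rest of Section 7 likewise sets stability, washout or exclusion conditions for entry. Nothing covers changes from day 0 to week 8, and Section 11.8 does not list a UC drug change as a reason for removal.

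**Link to the MTD.** Section 9.4 first requires "a minimum of 6 subjects have been evaluated, with fewer than 2 evaluable subjects in 6" having a DLT. It then adds that "at least 1 patient should meet the criteria for response or remission for it to be considered the MTD". Section 15 names the MTD as the primary endpoint.

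**Early removal.** Section 11.8 includes among its grounds for removal "The development of toxic megacolon or colitis requiring immediate surgical intervention"; Section 9.5 says that this event is not a DLT. Section 9.4 states: "Subjects will be considered unevaluable for DLT if they are removed from the study or die without developing DLT" before at least 8 weeks of IL-2. It continues: "If there are fewer than 3 evaluable subjects in a cohort, additional subjects will be added at that dose level". Sections 14 and 15 name no analysis set for response and no rule for a subject without a week 8 Mayo score.

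**The concern.** The trial is uncontrolled, and the Mayo score cannot tell improvement on IL-2 from improvement on an added or increased UC drug. In most phase I trials this would affect only a descriptive secondary endpoint. Here a single responder is a condition for declaring the MTD, so one subject whose corticosteroid was raised at, say, week 3 could decide whether the condition is met. Section 4.1 itself reports that corticosteroids induce remission in over half of the patients who need them. Those were newly diagnosed patients, so the figure may not carry over, but it shows that added therapy can move the endpoint.

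A smaller matter concerns the response rate. A subject removed without a DLT before 8 weeks is unevaluable for DLT and may be replaced, and has no stated place in the response denominator. If the rate is computed in those with a week 8 score, some of the clearest treatment failures drop out of it.

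**Working it through.** **The plan's own figures.** With true DLT rate p, the escalation probability is (1-p)^3 + 3p(1-p)^2 × (1-p)^3. At p = 0.10 this is 0.729 + 0.243 × 0.729 = 0.906; at p = 0.50 it is 0.125 + 0.375 × 0.125 = 0.172. All six entries of Table 6 reproduce. The stated ±26% is 1.645 × sqrt(0.25/10) = 0.260. These figures concern DLT and toxicity only; none covers response or the responder condition in 9.4.

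**Drug-change route into the 9.4 condition.** Inputs:
- n = 6, the minimum evaluated at the MTD (Section 9.4).
- f = proportion with a UC drug started or increased before week 8. Not in the documents; assumed 10-30%.
- r = proportion of those who then meet 14.4.1 or 14.4.2. Not in the documents; assumed 30-50%.
- q = response probability among subjects without a change. Assumed 0 first, then 10%.

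Subjects are taken as independent. If responses after a change count, the response probability per subject is p = q(1-f) + f × r. If they do not count, it is q(1-f). The condition is met with probability 1 - (1-p)^6.

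With q = 0:

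| f | r | p = f × r | Condition met, counted | Condition met, not counted |
|---|---|---|---|---|
| 10% | 30% | 0.03 | 0.167 | 0 |
| 10% | 50% | 0.05 | 0.265 | 0 |
| 20% | 30% | 0.06 | 0.310 | 0 |
| 20% | 50% | 0.10 | 0.469 | 0 |
| 30% | 30% | 0.09 | 0.432 | 0 |
| 30% | 50% | 0.15 | 0.623 | 0 |

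With q = 10%:
- f = 10%, r = 30%: p = 0.09 + 0.03 = 0.12, so 1 - 0.88^6 = 0.536 if counted, against 1 - 0.91^6 = 0.432 if not.
- f = 30%, r = 50%: p = 0.07 + 0.15 = 0.22, so 1 - 0.78^6 = 0.775 if counted, against 1 - 0.93^6 = 0.353 if not.

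**Denominator of the response rate.** Take 4 responders among 10 completers (assumed): 4/10 = 40%. With 1, 2, 3 or 4 removed subjects counted as non-responders, the rate is 4/11 = 36%, 4/12 = 33%, 4/13 = 31% or 4/14 = 29%.

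**The case against.** The strongest reply is that the plan is silent rather than wrong. No sentence says that a response after a drug change counts. The only express permission to add other drugs, in Section 9.7, concerns extended treatment after week 8, so one could infer that changes before then were not expected. That stands against any claim that the plan deliberately credits such responses. It does not close the gap: 9.7 does not say how an earlier change is scored, Section 11.8 does not remove the subject, and the definitions in 14.4 applied as written make the subject a responder.

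A reader might also infer more than the documents support on four points:

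- **That removed subjects disappear.** Section 14.3 reports numbers enrolled and completed. A subject with a DLT stays evaluable, and 9.4 treats intolerable lower-grade toxicity that prevents completion as equivalent to a DLT. The evaluability and replacement rules concern DLT, and no text limits response to completers; that is only the likely reading.
- **That any worsening of colitis leads to removal.** Section 11.8 names toxic megacolon or colitis needing immediate surgery, under a lead-in requiring possible relation to IL-2 or subject preference. Lesser worsening could lead to removal only through withdrawal or physician discretion.
- **That the missing denominator affects the MTD.** It cannot: adding non-responders never changes whether at least one subject responded.
- **That every response unrelated to IL-2 is at issue.** Spontaneous improvement can also satisfy the condition, and the change proposed here would not remove it.

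It may also be said that Section 9.3 and Table 2 identify the MTD without mentioning a responder. Section 9.4 presents the condition as an additional requirement, so the passages need reconciling, but the condition is in the plan.

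**Conclusion.** The concern holds as a gap in specification with a direct route to the primary endpoint. As written, a response that follows a UC drug started or increased before week 8 can satisfy the responder condition in 9.4. With no true IL-2 effect and the assumed rates, that happens with probability 0.17-0.62 among 6 subjects, against 0 if such responses do not count. With a true response of 10%, the range is 0.54-0.78 against 0.35-0.43. The documents give no rate of drug changes or of response after them, so these figures show sensitivity and are not predictions.

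The unspecified response set is a lesser point, confined to a secondary endpoint. If the rate is computed in completers it is biased upward, by 4 to 11 percentage points in the example above with 1 to 4 removed subjects.

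**What to change.** In Section 14.4, state that response, remission and mucosal healing are reported by dose level among all subjects who received at least one dose. State that a subject with no week 8 Mayo score, or with a UC drug newly started or increased between day 0 and week 8, counts as not achieving the outcome. Apply the same rule to the responder condition in 9.4, and show completers as a supplementary result.

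The cost is a few sentences, a somewhat lower reported response rate, and one addition to data collection. Section 11 lists medical history at visits but no explicit concomitant-drug record, so UC drug changes would have to be recorded. The rule may also discard a genuine IL-2 response in a subject whose drugs changed. At a true response of 10%, the chance of meeting the condition falls from 1 - 0.9^6 = 0.47 with no drug changes to 0.35-0.43 under the assumed rates of change. The rule governs analysis only and places no restriction on clinical management.
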